## 1. Introduction

#### 1.1. Background

Neonatal jaundice is a condition in newborns with elevated levels of the waste product bilirubin, also known as hyperbilirubinemia. It is primarily caused by a combination of the rapid turnover of red blood cells and the immature liver functions in the newborn. Neonatal jaundice affects approximately 60 to 80 % of newborns but is usually self-limiting and harmless. The condition is still potentially dangerous because bilirubin can accumulate in the basal ganglia of the brain, where it can cause permanent brain damage. Such brain damage, better known as kernicterus, can manifest as cerebral palsy, deafness, language difficulty, or in the worst cases, be fatal. 

*Bhutani et al.* estimated the incidence and impairment of neonatal jaundice for 2010 and concluded that failure to manage hyperbilirubinemia results in 114 100 avoidable neonatal deaths and many newborns who grow up with severe disabilities.  Three-quarters of these deaths are estimated to occur in the poorest regions of the world; sub-Saharan Africa and South Asia. Neonatal jaundice is one of the top three leading causes of death among newborns in sub-Saharan Africa. 

The main challenge in reducing the burden of neonatal jaundice is to identify children at risk at an early stage so that effective treatment can be given at an early stage.  Treatment of hyperbilirubinemia is usually done by phototherapy and, in some extreme cases, by blood transfusion. In some areas, sunlight is an optional treatment. 

Standard detection of neonatal jaundice varies in different countries. In Denmark, all infants are screened by transcutaneous bilirubinometers (TcB). The limit for when to measure total serum bilirubin (TSB) based on cutaneous bilirubin depends on the TSB standardization and which type of cutaneous bilirubinometer is used (BiliCheck/Minolta) in the individual department.  In African countries, however, detection of neonatal jaundice usually includes a clinical risk evaluation by visual assessment (VA) and sometimes a diagnostic blood sample to measure the level of total serum bilirubin (TSB).

In cases of high bilirubin levels, most countries apply subsequent capillary/venous samples for follow-up and to determine the need for therapy. Invasive blood sampling is linked to stress, pain, and substantial blood loss. Moreover, there is an increased risk of infections.

VA of neonatal jaundice is often based on the cephalocaudal progression of the yellowness using Kramer's scale, which assumes that a higher number corresponds to an increased level of serum bilirubin (Figure 1). This is the first-step screening option where other types of equipment are lacking.  Several studies have shown that VA is not a sufficient indicator on its own and unreliable as a screening tool for further testing. 

[figure not shown]

Fig. 1 Kramer's scale

To reduce the need to draw blood from the newborn, non-invasive devices that measure bilirubin concentration by shining light through the skin, such as transcutaneous bilirubinometers (TcB), have been developed.  TcB is one of the methods recommended by the American Academy of Pediatrics for the assessment of the risk of hyperbilirubinemia of newborns before discharge.  It is a safe, non-invasive method, and some studies have shown that its use can reduce the number of blood draws by 38,5%.  TcB shows a good correlation with blood samples, also in different ethnicities.  However, this is only true for the *BiliCheck* bilirubinometer. The *Minolta* bilirubinometer shows a higher transcutaneous bilirubin estimation in dark-skinned infants than in light-skinned infants. Additionally, it underestimates transcutaneous bilirubin when higher TSB levels are present. 

Lab equipment for TSB measurements and TcB devices is expensive, with a price range from 6.000 to 10.000 US dollars, thus making them practically unavailable in low-income countries. Because most deaths due to neonatal jaundice occur in low-income countries, there is a significant unmet need for simple, reliable, and affordable technologies to identify at-risk newborns. Mobile health, or mHealth, is an area with increased focus, as cell phone technology and smartphones are found worldwide, also in regions with scarce resources. This has given hope for new affordable solutions for global health. 

Picterus AS is a private limited liability company founded in Trondheim, Norway. They have developed a new smartphone app, Picterus Jaundice Pro (Picterus JP), that combines previous research on the bio-optics of jaundice in newborn skin with a mHealth approach.  Picterus JP uses an algorithm based on color analysis of a digital image to estimate the bilirubin levels in the blood, together with a unique color calibration card to adjust for different light conditions and the automatic adjustments in the phone (figure 2).

[figure not shown]

Fig. 2 Workflow of Picterus JP system. A) A photo of the newborn is taken, B) colors from the calibration card are used to calibrate the image, C) calibrated colors are compared with an extensive database of color- and bilirubin pairs, and D) the matching bilirubin estimate is presented to the user.

Picterus JP has been tested in 350 Caucasian and 170 Latin-American newborns, with mainly parents' skin types 1 to 4 according to the Fitzpatrick scale (Figure 3) and skin color 1 to 3 according to Neomar's neonatal skin color scale (Figure 4).  $^{20,21}$  The studies showed a Pearson correlation index of 0.83 to 0.88 and sensitivity of 90 to 100% to detect newborns with severe jaundice, defined as TSB above 250 µmol/L and specificity of 70 to 80%.

However, there is still uncertainty about how Picterus JP works in newborns with high melanin content (Asian and African population / Neomar's scale 4). Melanin could potentially influence the results, as it is one of the essential absorbers of light in the skin. However, melanocytes are immature at birth, and melanin levels in the skin are lower in newborns compared to adults.

Fig. 3 Fitzpatrick scale

Fig. 4 Neomar's skin color scale for newborns 

#### 1.2. Problem statement

Picterus performed a pilot study in Uganda from December 2019 to March 2020, which included 167 newborns. Results showed a Pearson correlation index of 0.59 between TSB and the Picterus image estimate, a sensitivity of 66%, and a specificity of 94%, when the cut-off was set to 250  $\mu$ mol/L. Only six newborns had bilirubin levels higher than 250  $\mu$ mol/L. It was concluded that more data is needed to optimize the performance of the tool for dark skin, including spectrophotometric measurements of skin color reflectance and newborns with higher bilirubin levels.

Currently, there is a running project in Uganda where data is collected from newborns with a broader range of bilirubin levels and high melanin content. Additional measurements of skin color reflectance with a spectrophotometer are made to adjust the Picterus JP algorithm and optimize the app performance. However, more data is needed to determine the adequacy of the app. Therefore, collecting data from different populations, such as in Botswana, will be valuable.

#### 1.3. Purpose of study

This study will be conducted at a hospital in Botswana, where we aim to collect data from newborns with a broader range of bilirubin levels and high melanin content in a different population than in the Uganda study.

#### 1.4. General Objective

The general objective is to investigate the use of Picterus JP in a population with high melanin content in the skin.

#### **1.5. Specific Objectives**

The specific objectives of this study are:

- i. To assess the correlation between estimations of bilirubin obtained by Picterus JP with TSB, and TcB, in newborns with high melanin content in the skin.
- ii. To determine the accuracy of Picterus JP used as a screening tool to identify high levels of bilirubin in newborns with melanin content in the skin.

#### 1.6. Scope of study

The study will be conducted in the neonatal unit (NNU) and the postnatal ward (4G) at Princess Marina Hospital in Gaborone, the capital of Botswana.

#### 1.7. Justification

We hypothesize that the Picterus JP will offer bilirubin level estimates that are highly correlated to bilirubin levels measured in blood samples in a population in Botswana. Following our hypothesis, the short-term goal for this project is to demonstrate that this screening method can be used to identify children with severe neonatal jaundice independent of skin color. Thus, providing a cheaper, patient-friendly, and more readily available means of neonatal jaundice detection.

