#### 2.6. Data collection

Following informed consent, background data such as birth weight, age on examination, gestational age, and type of feeding will be obtained. Gestational age will be based on ultrasound determination and the last normal menstruation period (LNMP). The skin type of the infant will be classified according to the newborn Neomar's scale score (Figure 4).

Transcutaneous bilirubin estimates will be performed over the sternum of the infant. A Dräger Jaundice Meter JM-105 will be used in this study.

Skin reflectance will be done using a CE-marked portable Konica Minolta spectrophotometer CM-700d. The spectrophotometer readings will be used to adjust the existing algorithm from Picterus to African skin and thereafter bilirubin estimates from the taken images will be determined.

The Picterus calibration card will be fixed in place with a disposable back sticker on the newborn's chest with the hole of the card placed over the infant's sternum. A validated smartphone with Picterus JP will then be used to collect digital images, as shown below. Once the phone is aligned with the card, two sets of 6 images of each newborn will be captured, 3 with flash and 3 without flash. After all the images are obtained, a unique ID will be displayed on the smartphone. This ID will be recorded on the case report forms and later used to pair clinical data and digital images.

Fig.5 Picterus JP image procedure

A blood sample to determine TSB will be obtained within 60 minutes of obtaining the images and processed at the Department of clinical biochemistry in the hospital laboratory. In addition, TSB will be measured with neonatal bilirubin analyzer Neo-Bil Plus from DAS to assess the quality of the equipment. For the hospital laboratory analysis, 1 ml of blood is required and will be obtained either by venous puncture or heel prick. An additional 10  $\mu$ l volume of blood will be collected in a heparinized capillary tube for analysis in the Neo-Bil Plus equipment.

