#### 2.7.2. Statistical analysis

The bilirubin estimates from the images taken will be determined. The images will be compared to the TSB, NeoBil and TcB measurements using the Pearson correlation coefficient. Sub-analysis for the different skin colors, gestational ages, days of life, and bilirubin levels will be performed for the TSB and image estimate. Sensitivity and specificity analysis will be calculated for different cut-off values using the ROC analysis. Systematic over- or underestimation of bilirubin levels will be evaluated using Bland-Altman plots. To avoid bias, the developer of the product – Picterus AS – will not be involved in statistical work-up or even see the raw data.

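### The short-term goal in section 1.7, detection independent of skin colour, exceeds the formal objectives and cannot be shown by this design

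*Protocol*

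**What the plan says.** Section 1.7 (Justification) hypothesises a high correlation with blood values in a Botswana population, and then gives the short-term goal for the project: to "demonstrate that this screening method can be used to identify children with severe neonatal jaundice independent of skin color".

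The formal aims are narrower. The general objective (1.4) is "to investigate the use of Picterus JP in a population with high melanin content in the skin". Specific objective i (1.5) concerns correlation "in newborns with high melanin content in the skin", and objective ii concerns screening accuracy in newborns described in nearly the same terms. Section 1.6 fixes the setting: "The study will be conducted in the neonatal unit (NNU) and the postnatal ward (4G) at Princess Marina Hospital in Gaborone". No lighter-skinned group is planned.

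Section 2.6 states that "The spectrophotometer readings will be used to adjust the existing algorithm from Picterus to African skin", and that the image estimates are determined after that. The same section records a Neomar score for each infant. Appendix IV (standard operating procedure) calls for three reflectance measurements per infant with the CM-700d.

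Section 2.7.2 contains the only planned analysis of skin colour: "Sub-analysis for the different skin colors, gestational ages, days of life, and bilirubin levels will be performed for the TSB and image estimate". The sample size in 2.3 rests on limits of agreement, one AUC and three bilirubin bands. Skin colour does not enter it.

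**The concern.** Independence from skin colour is a statement about a contrast: the same algorithm version has to perform alike across a range of skin colours. Showing it requires either groups that span the range, or enough measured variation within the sample, together with a stated estimate of how the error changes with skin colour.

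The plan has no group outside the high-melanin population. The version tested is tuned to that population's skin, and the results in 1.1 from 350 Caucasian and 170 Latin-American newborns predate the tuning. Within the sample, skin colour is one of four sub-analysis factors, with no stated estimate of dependence. A subgroup difference that fails to reach significance would not be evidence of independence.

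The risk is a conclusion wider than the data. It matters because section 1.2 reports weaker results in the Uganda pilot (r = 0.59, sensitivity 66%) than 1.1 reports in mainly lighter skin (r = 0.83 to 0.88, sensitivity 90 to 100%). Section 2.12 plans publication and says the results bear on potential validation.

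**Working it through.** **1. The plan's own precision figure.** Section 2.3 gives n = 150, s = 35 µmol/L and SE = √(3s²/n).

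- SE = √(3 × 35² / 150) = 4.95 µmol/L.
- Multiplied by the t quantile on 149 df (1.976) this gives 9.8 µmol/L, as stated.

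The figure reproduces. It is the precision of the overall limits of agreement and says nothing about skin colour.

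**2. What subgroup correlations could show.** Inputs: r = 0.84 (Norwegian study of 134 Caucasian newborns, Appendix V, 1.1); r = 0.59 (Uganda pilot, 1.2); r = 0.75 (assumed, a moderate drop). The Protocol gives no expected Neomar distribution, so group sizes of 50 and 20 are assumptions.

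Fisher z: atanh(0.84) = 1.221, atanh(0.59) = 0.678, atanh(0.75) = 0.973. For two groups of n each, SE = √(2/(n − 3)) and power ≈ Φ(difference/SE − 1.96).

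| n per group | SE | 0.84 vs 0.59 (difference 0.544) | 0.84 vs 0.75 (difference 0.248) |
|---|---|---|---|
| 50 | 0.206 | z = 2.63, power 75% | z = 1.20, power 22% |
| 20 | 0.343 | z = 1.58, power 35% | z = 0.72, power 11% |

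For a single subgroup with r = 0.84, the 95% interval is 0.73 to 0.91 at n = 50 and 0.63 to 0.93 at n = 20.

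**3. Severe cases.** The 1.7 goal concerns severe jaundice. At the Uganda pilot rate (6 of 167 above 250 µmol/L, section 1.2), 150 infants give 150 × 6/167 = 5.4 cases. If 5 of 5 were detected, the exact lower 95% limit for sensitivity is 0.025^(1/5) = 48%. At an assumed rate of 10% there would be 15 cases, and 15 of 15 gives 0.025^(1/15) = 78%. These limits apply before any split by skin colour. The Botswana rate is not given.

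**4. What a regression on reflectance could show.** Regress (image estimate minus TSB) on reflectance in all 150 infants. Per SD of reflectance, the 95% half-width is 1.96 × SD/√150.

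- SD 35 (the St. Olav value in 2.3): 1.96 × 2.86 = ±5.6 µmol/L.
- SD 50 (assumed): 1.96 × 4.08 = ±8.0 µmol/L.

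Adjustment for TSB divides the half-width by √(1 − ρ²), where ρ is the correlation of reflectance with TSB. At an assumed ρ of 0.5, with the residual SD unchanged, these become ±6.5 and ±9.2. The ±5.6 is a best case, because the SD of 35 comes from Caucasian newborns.

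**The case against.** **The sentence is only in the Justification.** It is tied to no endpoint, test or sample size. Sections 1.3 to 1.5 are confined to high-melanin newborns, and the hypothesis in 1.7 itself refers to Botswana. In context the words may mean little more than that the tool should also work in dark skin. This stands, and it limits the point: the objectives are sound and one stated goal overreaches them. A reader might infer that independence from skin colour is what the study was set up to settle; 1.3 to 1.5 do not support that. The sentence still needs changing, because it says what this project is to demonstrate, while 1.8 separately gives the long-term goal.

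**Subgroups are not blind.** A reader might infer that almost any skin-colour difference would look null. That is wrong. At 50 per group the documents' own contrast, 0.84 against 0.59, gives z = 2.63. The weakness is with moderate differences or small groups.

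**Analysis detail may sit in an unseen SAP.** Section 2.7.2 does not say which measure defines skin colour, does not limit the sub-analysis to correlation, and also plans Bland-Altman plots. This stands too. The regression is therefore an addition, not the repair of an error, and the sub-analyses can remain as description.

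**Earlier lighter-skin data might still be comparable.** The Protocol does not say that the adjustment would change estimates in lighter skin. Nor does it plan to check, so comparability would have to be assumed.

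**Conclusion.** The point holds as a mismatch between a stated goal and the design. With one high-melanin population, an algorithm adjusted to that skin, no run of that version in lighter-skinned newborns and only sub-analyses by skin colour, the study cannot demonstrate independence from skin colour. It can estimate performance in newborns with high melanin content in Botswana, which is what 1.4 and 1.5 ask for.

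The size depends on assumptions. The group sizes, the r of 0.75 and the SD of 50 are not in the Protocol. Under them, subgroup power runs from 75% for a large difference at 50 per group down to 11% for a moderate one at 20 per group. A regression in all infants would give the slope to about ±5.6 to ±8 µmol/L per SD of reflectance, and wider if reflectance and TSB are correlated.

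Even that slope describes only the range of skin colour present in the sample. A slope near zero would not extend to lighter skin.

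**What to change.** 1. **Section 1.7.** Restate the short-term goal as performance of the tool in newborns with high melanin content in Botswana, in line with 1.4 and 1.5.

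2. **Section 2.7.2.** Keep the skin-colour sub-analyses as description. Add a linear regression of (image estimate minus TSB) on one reflectance index from the CM-700d readings, adjusted for TSB, in all infants, reporting the slope and its 95% CI. Name the index beforehand, since the Protocol does not say which wavelength or summary of the readings would be used.

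3. **Both algorithm versions.** Run the regression on the unadjusted as well as the adjusted algorithm. The readings are used to tune the adjusted version, so its result alone would be partly circular and could hide a melanin-related bias. Section 2.8 says all image estimates are made after data collection, so both versions can be applied to the same images.

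The cost is a narrower claim and one extra analysis on measurements already planned for every infant. Recruitment, visits and sample size do not change.

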#### 1.8. Significance of study

The long-term goal is that with the implementation of the app, the identification of newborns with jaundice will be improved and, thus, referred at an earlier stage for diagnostics and treatment. This would lead to reduced neonatal morbidity, mortality, and fewer children with permanent disabilities following hyperbilirubinemia, also in patients with high melanin content, such as the population in Botswana. The clinicians at Princess Marina Hospital will benefit from this as they will be equipped with a cheap, readily available application for detecting neonatal jaundice.

# 2. Methodology

#### 2.1. Study design

The study will be a diagnostic accuracy cross-sectional study with quantitative methods of data collection.

#### 2.2. Study setting

The study will be conducted in the neonatal unit (NNU) and the postnatal ward (4G) at the Princess Marina Hospital (PMH) in Gaborone, Botswana. PMH is a provincial, government-funded hospital and the largest referral hospital in Botswana.

The hospital offers preventive, curative, and rehabilitation services and serves as a primary, district, and tertiary hospital. The hospital has an in-patient capacity of more than 500 beds and handles a minimum of 2500 outpatients daily.

The NNU has 38 beds distributed in 5 cubicles, is often overcrowded, and receives neonates from the on-site labor ward and babies referred from the surrounding clinics and district hospitals. On estimations from prof. [name], who is employed at the department, there are approximately 100 neonatal admissions per month (ranging from 82-127 monthly in 2017-2022), including patients who need intensive care on ventilators. Of these are 47% girls and 53% boys. The total mortality is 18% of the admitted infants. The estimated gestational age and weight of the patients at the NNU can be found in Table 2 and Table 3, respectively, and are based on the admitted infants in May 2022. In the postnatal ward, there are approximately 500 mothers admitted monthly (ranging from 498-508 monthly in May-July 2022), including normal and c-section deliveries. 

#### Date of document: March 1, 2023

Gestational age	n	%
< 28 weeks	13	14.1
28-29 weeks	8	8.7
30-31 weeks	8	8.7
32-34 weeks	14	15.2
35-36 weeks	14	15.2
37-40 weeks	29	31.5
>40 weeks	6	6.5
Total	92	100

Weight	%
<1000 g	10
1000-1500 g	20
1500-2500 g	25
2500-4000 g	40
>4000 g	5
Total	100

Table 2: Estimated gestational age at NNU

#### 2.3. Study population and sample size calculations

The study population will comprise 150 newborns from the Neonatal Unit and the postnatal ward at Princess Marina Hospital, a number determined by a sample size calculation based on standard errors of the 95% limit agreement, as described by Bland and Alman.

The standard error of the 95% limit of agreement is given by  $\sqrt{\frac{3\times s^2}{n}}$ , where *s* is the standard deviation of the differences between measurements by the two methods, and *n* is the sample size.

The study performed at St. Olav Hospital showed a standard deviation (*s*) of the difference between bilirubin estimates from digital images to blood samples of 35  $\mu$ mol/L.  A sample size (*n*) of 150 participants will then give the confidence interval of the limits of 9,8  $\mu$ mol/L, a relevant size for clinical use.

The study objective of this study is two-folded. First, we wish to determine the correlation between TSB measurement and Picterus image estimate of serum-bilirubin. Second, we wish to determine the accuracy of the Picterus App used as a screening tool.

The study conducted by Aune et al. found an AUC of 0.925. To calculate the sample size for this study we used the used the EasyROC tool, by setting an AUC of 0.9, a significance level of 0.5 and a power to 0.8. This gave the suggested sample size of 12 infants. In order to get a sufficient result for all bilirubin levels, we decided to apply our pilot data to see how many subjects were needed to receive a sample of 12 in three different groups; <100  $\mu$ mol/L, 100-200  $\mu$ mol/L and >200  $\mu$ mol/L. Through this calculation we came to the number of 115 infants.

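### The ROC sample size prints a significance level of 0.5 that does not yield the stated 12 infants on the likeliest reading, and 12 per bilirubin band does not size accuracy at each level

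*Protocol*

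**What the plan says.** Section 2.3 of the protocol has two calculations. The first sets enrolment at 150 from the precision of the limits of agreement. The second follows the statement of the accuracy aim, "Second, we wish to determine the accuracy of the Picterus App used as a screening tool". It uses an ROC sample size tool "by setting an AUC of 0.9, a significance level of 0.5 and a power to 0.8" and reports: "This gave the suggested sample size of 12 infants". The planning AUC is supported by an earlier study's AUC of 0.925. The null AUC, the sidedness, the ratio of cases to controls and the bilirubin cut-off that defines a case are not given.

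The section then continues "In order to get a sufficient result for all bilirubin levels": pilot data were used to find "how many subjects were needed to receive a sample of 12 in three different groups", namely total serum bilirubin (TSB) below 100, 100 to 200 and above 200 µmol/L. The result is 115 infants.

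Section 2.7.2 states "Sensitivity and specificity analysis will be calculated for different cut-off values using the ROC analysis", and also "Sub-analysis for the different skin colors, gestational ages, days of life, and bilirubin levels will be performed" for TSB against the image estimate.

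**The concern.** There are two separate problems.

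- **The printed input.** A significance level of 0.5 is not a credible design value, and a reader who enters it under the usual assumptions does not get 12.
- **The reuse of 12.** A number obtained for one overall test of discrimination is carried into each TSB band and described as sufficient at every level. The requirement does not transfer, because TSB is the reference standard that separates cases from controls.

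This is the only calculation the protocol offers for the accuracy objective (section 1.5, objective ii). As worded, a reader could believe that accuracy has been sized at low, middle and high bilirubin. At most, the step ensures that some infants fall in each range.

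**Working it through.** **Inputs.** From section 2.3: AUC 0.9, power 0.8, printed significance level 0.5, stated result 12. Assumed because not stated: null AUC 0.5 and a 1:1 ratio of cases to controls; both one- and two-sided tests were tried.

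**Step 1: can 12 be reproduced?** For one AUC against a null,

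n per group = [z(α)·√V(0.5) + z(power)·√V(0.9)]² / (0.9 − 0.5)²

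with the binormal variance at 1:1, V = 0.0099·exp(−A²/2)·[(5A² + 8) + (A² + 8)] and A = 1.414·z(AUC).

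This gives V(0.5) = 0.1584 (root 0.398) and V(0.9) = 0.0684 (root 0.2616). The power term is 0.8416 × 0.2616 = 0.220.

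- Level 0.5, two-sided: (0.6745 × 0.398 + 0.220)² / 0.16 = 1.49 per group
- Level 0.05, two-sided: (1.960 × 0.398 + 0.220)² / 0.16 = 6.25 per group
- Level 0.05, one-sided: (1.645 × 0.398 + 0.220)² / 0.16 = 4.78 per group
- Level 0.5, one-sided: z(α) = 0, so 0.220² / 0.16 = 0.30 per group

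| Level | Sides | Total, unrounded | Total, each group rounded up | Total, finite-sample Hanley-McNeil |
|---|---|---|---|---|
| 0.5 | two | 3.0 | 4 | 4 |
| 0.5 | one | 0.6 | 2 | 2 |
| 0.05 | two | 12.5 | 14 | 14 |
| 0.05 | one | 9.6 | 10 | 12 |

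The stated 12 sits with 0.05, not 0.5. One-sided 0.05 with two controls per case gives exactly 12. At 0.5 two-sided, ratios of 2:1 and 3:1 give rounded totals of 6 and 8. Only ratios of 4:1 or more come within two of 12, and only through rounding up (10 at 4:1, where the unrounded total is 5.1; 11 at 10:1). As a check by simulation with an exact Mann-Whitney test, 6 + 6 infants have about 75% power at 0.05 and about 99% at 0.5.

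**Step 2: does 12 carry over to a band?** On the reading above, 12 is about 6 cases plus 6 controls. Take the 250 µmol/L cut-off that sections 1.1 and 1.2 use for earlier studies. Every infant below 100 and every infant at 100 to 200 is then a non-case, so neither band has an AUC. The 80% power belongs to one pooled test and not to any band.

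**Step 3: what do 12 infants give?**

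- Exact (Clopper-Pearson) 95% intervals for sensitivity or specificity: 11/12 gives 61.5% to 99.8%; 10/12 gives 51.6% to 97.9%.
- Correlation, by Fisher z: atanh(0.59) ± 1.96/√(12 − 3) = 0.678 ± 0.653, which back-transforms to 0.02 to 0.87. The 0.59 is the overall pilot value in section 1.2 ("Results showed a Pearson correlation index of 0.59 between TSB and the Picterus image estimate") and serves only as an illustration; a value within a band could differ.

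**Step 4: what does the pooled sample support?** Twelve in 115 implies that the scarcest band holds 10.4% of infants. At 150 that is 150 × 12/115 = 15.7, about 16. The document does not say which band drove the 115. If it was the band above 200, and that band defines the cases, the Hanley-McNeil power of AUC 0.9 against 0.70 (two-sided 0.05) is about 68% with 12 cases and 103 controls, and about 83% with 16 and 134.

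Precision at 150 depends on the case rate. None is given for Botswana, so the rates below are assumptions:

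| Assumed case rate | Cases | Example sensitivity, exact 95% interval | SE of AUC 0.9 |
|---|---|---|---|
| 5% | 8 | 7/8: 47% to 99.7% | 0.074 |
| 10% | 15 | 13/15: 60% to 98% | 0.054 |
| 20% | 30 | 27/30: 73% to 98% | 0.039 |
| 30% | 45 | 40/45: 76% to 96% | 0.032 |

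**The case against.** The strongest reply is that this is a dropped digit with no consequence. At 0.05 the 12 is recovered, no analysis uses the value, and the 150 comes from elsewhere and exceeds 115. That is true of the consequence, but a design input that does not lead to its stated result still needs correcting.

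A second reply is that the failure to reproduce depends on assumed inputs. With a null AUC of 0.70, a two-sided level of 0.5 and a 1:1 ratio, the same formula gives 5.69 per group, which rounds to exactly 12 in total. This stands as a reason not to claim certainty about what was entered. It does not make the text sound, because it would mean that a 50% significance level was really intended.

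A third reply is that the bands are only a rule for spreading recruitment across low, middle and high bilirubin, and that no ROC analysis by band is planned. That reading is reasonable, and nothing in section 2.7.2 contradicts it. But section 2.3 offers the step as giving a sufficient result at all levels and borrows its number from an AUC power calculation. If spread is all that is meant, the text should say so.

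Finally, expected precision may be set out in a statistical analysis plan that is not shown. That is fair, so adding it here is optional. The two statements in section 2.3 are wrong as printed wherever further detail sits.

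**Conclusion.** The concern holds on both parts. With a null AUC of 0.5 and a 1:1 ratio, the printed level gives 3 to 4 infants two-sided (1 to 2 one-sided), not 12, while 0.05 gives 10 to 14. The likeliest explanation is a misprint for 0.05, which the document alone cannot confirm because the null, sidedness and ratio are missing.

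The per-band claim fails whichever level was used. A total sized for one overall AUC test gives no assurance within a TSB band, and 12 infants leave an interval for sensitivity or specificity nearly 40 percentage points wide even at 11/12 (99.8 − 61.5 = 38.3).

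The effect on the design is limited. Enrolment stays at 150, and the pooled sample supports more than a test against chance. What is wrong is the stated input and the claim of sufficiency at every level. Both should be corrected.

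**What to change.** Reword the ROC paragraph of section 2.3:

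1. Replace 0.5 with the significance level actually entered (0.05 if that is what was used), and state the null AUC, the sidedness and the case-to-control ratio.
2. Remove the claim of sufficiency at all bilirubin levels, or limit it to representation across the range.
3. If the null entered was 0.5, say that the 12 was sized against chance. State that the 12-per-band step does not size sensitivity or specificity.
4. Preferably, add the precision expected from 150 infants for sensitivity and AUC at the intended cut-off or cut-offs, with the assumed case rate shown as a range.

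The cost is one paragraph of text. No infants are added and no analysis changes; the stated justification for the accuracy aim becomes less favourable.
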